#### Table 3. List of potential effect modifiers

### 5.7 Sensitivity and additional analyses

The following analyses will be conducted for primary and selected secondary outcomes, and the results will be compared.

#### Sensitivity analyses:

- Analyses using Generalised Estimating Equations with an independence correlation structure and robust standard errors to minimise potential bias due to informative cluster size [13].
- Cluster-level analyses
- Analysis of the intervention effect on "no pain or effective pain management strategy at LMP" as a sensitivity analysis for secondary outcome 3 in case of an intervention effect on any reported pain.

#### Additional analyses:

- Analysis of participants in the closed cohort (described in sub-section 3.5)
- Estimation of the complier average causal effects based on school and individual-level definitions of intervention fidelity and intensity.

### 5.8 Exploratory analyses

We will undertake exploratory analyses of intervention effects on additional outcomes, including:

- School dropout, defined as having left a trial school without known enrolment in another school
- Educational attainment for each subject separately (English, biology, maths)
- SDQ internalising sub-scale
- MPNS sub-scales and school-specific items separately
- Subjective wellbeing (measured by life satisfaction and happiness)
- Experience of teasing
- Perception of school's support for menstrual health
- Knowledge of effective pain management strategies
- Mean score (out of 10) or proportion on social norms items

## 6 Statistical considerations

#### 6.1 Missing data

Survey and exam completion rates are expected to be high for girls, so only a small amount of missing data is expected and the primary analyses will be complete case. Sensitivity analyses will however be conducted for the primary outcomes using inverse probability weighting if there was substantial missing data.

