## 2 Study Design

### 2.1 Trial design

The study was a parallel-arm, cluster-randomised controlled trial with a mixed-methods process evaluation, and economic and policy analyses. Schools (clusters) were randomised 1:1 to immediate delivery of the MENISCUS intervention or optimised usual care (provision of government menstrual management readers and circular). Schools randomised to the optimised usual care arm were offered the intervention after the endline assessment (approximately 1 year after randomisation). In this SAP, the term "intervention" refers to immediate intervention, and "control" to optimised usual care (delayed intervention, delivered after endline).

Female students who joined the S2-S3 class cohort during the intervention delivery period were eligible to be recruited. This "open cohort" design accommodates the dynamic school population, as students may both join and leave the class cohort during the intervention period. In the pilot study, 82% of participants present at baseline were present at the endline survey 9 months later [6]. Primary and secondary outcomes for female students will be assessed among participants present at endline, adjusting for cluster-level mean baseline measures of the relevant outcome where available. Knowledge and attitudes among male students will be assessed through a closed cohort. Further details are described in section 3.4 below.

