### 5.2 Analysis of continuous outcomes

The intervention effect for each primary outcome (educational attainment and SDQ) and continuous secondary outcomes will be presented as the adjusted mean difference in the endline scores between arms with corresponding 95% confidence intervals (CI). The effects will be estimated using linear random-effects (RE) models using a random intercept for school to adjust for within-school clustering. The model will be adjusted for the cluster-level mean of the baseline outcome measure and stratification variables (district and high/low school-level UNEB score). Likelihood ratio tests (LRT) will be used to obtain p-values. The results will be presented as shown in Table A5.

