### 5.6 Effect-modification and mediation

Pre-specified potential effect modifiers are given in Table 3. In addition, we will assess baseline SDQ score and baseline UNEB exam score as individual-level effect-modifiers for the two primary outcomes, respectively.

Effect-modification for each of these variables with trial arm will be assessed for primary and selected secondary outcomes by fitting an interaction term with each variable and trial arm in the model. The strength of evidence (p-values) for effect-modification will be assessed using LRT.

We will also explore hypothesised causal pathways through mediation analyses specified in advance as part of the process evaluation.

Effect modifier	School/individual level	Measure
1. District	School level	Binary (Kalungu, Wakiso)
2. School ownership	School level	Binary (government, private)
3. Baseline UNEB exam z-score	School level	Binary (<0, ≥0)
4. S2 size (pre-intervention)	School level	Binary (median as cutoff: <59, ≥59)
5. School type (% boarding	School level	Binary (<50% boarding, >50% boarding)
students)		
6. Age group (at endline)	Individual level	Binary (median as cutoff)
7. Student type (day vs	Individual level	Binary (day, boarding)
boarding)		
8. Socio-economic status	Individual level	Binary (median as cutoff)

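### Primary effects rest on girls still present at endline, with no individual-level correction for who left and a weighting analysis that leavers may never trigger

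*SAP*

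**What the plan says.** - **Who is analysed.** Section 2.1: "Primary and secondary outcomes for female students will be assessed among participants present at endline". Section 3.5 limits the primary population to enrolled girls with endline survey or UNEB data. The female closed cohort is limited to baseline recruits still at the same school at endline.
- **Expected turnover.** Section 2.1, on the pilot: "82% of participants present at baseline were present at the endline survey 9 months later". Section 2.6 puts this trial's endline at about one year after randomisation.
- **Model.** Section 5.2: "adjusted for the cluster-level mean of the baseline outcome measure", plus district and high/low school UNEB score. All of these are school-level terms.
- **Missing data.** Section 6.1 expects high survey and exam completion, so "only a small amount of missing data is expected and the primary analyses will be complete case". A sensitivity analysis follows for the primary outcomes "using inverse probability weighting if there was substantial missing data".
- **Individual baselines.** Section 5.6 uses "baseline SDQ score and baseline UNEB exam score as individual-level effect-modifiers". The SAP names no other role for them.
- **Leavers.** Sections 3.4 and 4.1 provide for tracing, reasons for leaving, a by-arm description and a look at associated factors. Section 5.8 lists dropout as an exploratory outcome.

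**The concern.** Being present at endline is a post-randomisation event that the intervention could influence; the plan itself lists dropout as an outcome. Suppose the intervention keeps weaker or more distressed girls in school. The intervention arm's endline mean then includes girls whose counterparts have left the control arm, and the measured benefit shrinks. If selection runs the other way, the benefit is exaggerated. Adjusting for the school's baseline mean does not address which girls within a school stayed. The closed cohort conditions on the same event and has no different model, so it gives no independent check.

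The one planned correction depends on a trigger that is not defined. Section 6.1 is phrased around completion of the survey and exam, and under Section 3.5 a girl who has left is outside the analysis population. Completion among enrolled girls could be close to full while nearly a fifth of the baseline girls are gone, and the weighting would not run.

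**Working it through.** **1. The plan's own power (Section 2.3).** Effective n per arm = 30m / (1 + (m − 1) × 0.05).
- m = 60: 1800 / 3.95 = 455.7; SE = √(2/455.7) = 0.066 SD; power for 0.2 SD is 84.3% (noncentral t, 58 df). The plan states 84%.
- m = 40: 1200 / 2.95 = 406.8; SE = 0.070 SD; power 80.1%. The plan states 80%.

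Both figures reproduce. They are defined on girls at endline, so leaving is mainly a bias question and not a power question.

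**2. Size of turnover.** Pilot: 1 − 0.82 = 18% at 9 months. Assuming a constant rate, 1 − 0.82^(12/9) = 23% at 12 months.

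**3. When bias arises.** Let p be the share leaving in an arm and g the amount (SD) by which leavers fall below stayers on the outcome. Stayers then exceed the whole arm by p × g, so

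bias = p₁g₁ − p₀g₀ (1 = intervention, 0 = control).

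The SAP gives neither p by arm nor g, so these inputs are assumptions:
- Same p and same g in both arms: 0.
- 16% v 20% leaving, g = 0.2 to 0.8: −0.008 to −0.032 SD.
- 13% v 23% leaving, g = 0.2 to 0.8: −0.02 to −0.08 SD.
- 18% leaving in both arms, g = 0.2 v 0.5: 0.18 × (0.2 − 0.5) = −0.054 SD.

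The last line shows that equal leaving rates alone do not protect.

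**4. Simulation.** 60 schools × 50 girls, ICC 0.05, true effect 0.20 SD, baseline–endline correlation 0.6, 1500 runs per setting. School count, ICC and effect size are from Section 2.3; the rest is assumed.

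| Retention, control / intervention | School-mean adjusted | Individual baseline added | Weighted |
|---|---|---|---|
| 82.3 / 87.2% | 0.183 | 0.199 | 0.198 |
| 80.0 / 85.6% | 0.174 | 0.200 | 0.199 |
| 80.0 / 89.1% | 0.157 | 0.199 | 0.197 |
| 81.2 / 83.5%, different leavers by arm | 0.149 | 0.200 | 0.198 |
| 82.4 / 82.3%, same leavers | 0.202 | 0.202 | 0.201 |

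Attenuation in the first four rows runs from (0.20 − 0.183)/0.20 = 8.5% to (0.20 − 0.149)/0.20 = 25.5%. A separate run with log-odds of staying of 0.6–1.0 per SD of baseline score gave 0.183, 0.168 and 0.151 with the school mean. It gave 0.200–0.201 with the individual baseline.

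**5. Closed-form check and milder inputs.** If staying depends on baseline score, bias = correlation × (stayers' mean baseline, intervention − control).
- 82.5 v 87.4%, log-odds 0.6: 0.6 × (0.0726 − 0.0998) = −0.016, close to the simulated loss of 0.017.
- 80 v 84%, log-odds 0.6: 0.6 × (0.0915 − 0.1135) = −0.013 (about 7%).
- 80 v 84%, log-odds 0.3: 0.6 × (0.0474 − 0.0591) = −0.007 (3.5%).
- 81 v 83%, log-odds 0.3: 0.6 × (0.0504 − 0.0562) = −0.0035 (about 2%).

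Simulating 81 v 84% with log-odds 0.3 loses 0.006–0.009 SD, or 3–4.5%.

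**6. Against the design SE of 0.066.** A loss of 0.009 SD is 0.14 SE. A bias of 0.03 SD towards the null lowers power from about 85% (normal approximation) to 73%, and 0.05 SD lowers it to 62%.

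**The case against.** **Denominators.** A reader might infer that Section 6.1 contradicts the pilot figure. It does not. Section 6.1 concerns completion of the survey and exam; the 82% is the presence of baseline girls at endline. High completion among enrolled girls is compatible with 18% turnover, and the open cohort is the plan's deliberate answer to turnover. This stands. The two statements are in tension only because the plan never says whether a leaver counts as missing.

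**Individual scores.** A reader might also infer that the plan has decided against using baseline scores for correction. Section 6.1 lists no weight predictors, so the scores are neither named nor excluded. The fault is under-specification.

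**Existing safeguards.** Leavers are traced, described by arm and analysed for dropout, and Section 2.5 keeps the trial statistician masked. These steps would show unequal leaving, but they would not correct for it. A comparison of proportions can also miss arms that lose different kinds of girl at similar rates.

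**Chosen inputs.** The larger attenuations need 5–9 points of differential retention or arm-specific selection, with a fairly strong link between baseline score and staying. Milder inputs give 2–7%, small beside the SE. Individual adjustment recovers 0.20 because leaving in the simulation depends on measured baseline. Leaving driven by later distress would defeat both remedies. This stands and limits the claim.

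**Target and joiners.** Counting leavers as missing moves the question towards the baseline cohort. For girls who joined later, Section 3.3 mentions only socio-demographic data at recruitment. This is a fair reason to confine the weighting to a sensitivity analysis and to state how joiners are treated.

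**Conclusion.** The point holds as a risk that the plan leaves uncontrolled. Every planned female analysis conditions on presence at endline, no individual-level predictor of staying enters the main-effect model, and the single correction hangs on an undefined trigger that leavers may not activate. The illustrative simulations put the attenuation at about 3–25% of a 0.20 SD effect, and at zero if leaving is the same in both arms. These sizes rest on assumed retention by arm, an assumed link between baseline score and staying, and a baseline–endline correlation of 0.6; the SAP supplies none of them.

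A reader might go further and conclude that the primary effects are biased, or biased towards no benefit. The documents do not support that: they give no retention by arm and no comparison of leavers with stayers, and the direction depends on who leaves. The improvement is worth making because the data are already collected and the primary analysis need not change.

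**What to change.** 1. **Female closed cohort, both primary outcomes.** Add the girl's own baseline value of the outcome alongside the school mean. The same covariate can be added in the male closed cohort for precision; the gain in the simulations was small (SE 1–4% lower).
2. **Weighted sensitivity analysis, both primary outcomes.** Run it unconditionally. Fix in advance the denominator (all baseline-recruited girls, leavers counted as missing) and the predictors: baseline exam score, SDQ, age, boarding status and SES. Either restrict it to baseline-recruited girls or state that joiners receive weight 1. Keep the open-cohort analysis as primary.
3. **Section 6.1 wording.** Clarify that the expectation of little missing data refers to survey and exam completion among enrolled girls.

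Cost: a few sentences in the SAP and a little extra analysis. Limits: joiners lack individual baselines, so item 1 applies to the closed cohorts only, and neither method corrects leaving driven by unmeasured post-baseline factors.

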#### 6.2 Multiple testing adjustment

The two primary outcomes are considered independent due to different causal mechanisms, so an improvement in one without the other will be informative. According to FDA and EMA guidelines, we shall adjust the Type 1 error for multiple testing using the Benjamin-Hochberg (BH) procedure [14]. The procedure states that for the two primary outcomes considering a false discovery rate (FDR) of 0.05: 1) if the larger p-value  $\leq 0.05$ , then there is evidence for both end points; 2) if the larger p-value >0.05, then the smaller p-value should be  $\leq 0.025$  to show evidence for that endpoint, and 3) if the larger p-value >0.05, then there is no evidence for both endpoints. Despite this procedure, interpretation of the intervention effect will focus on effect sizes and confidence intervals rather than p-values.

For the secondary outcomes, specific inferences will be made for each individual null hypothesis and multiple testing adjustment will not be performed. Given the number of tests performed, the intervention effects will be interpreted with caution [15,16].

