### 2.3 Sample size

The sample size of 60 schools was based on an anticipated harmonic mean of 60 female participants per school at endline. This sample size provides 84% power to detect a standardised mean difference of 0.2 for continuous outcomes, assuming an intra-cluster correlation ( $\rho$ ) of 0.05 and type 1 error of 0.05. The effect size of 0.2 is that observed for the primary outcome of SDQ score for girls in the pilot [6] and is considered moderate for educational outcomes and hence of policy relevance. The harmonic mean was used to account for variation in school size. We have not adjusted the type 1 error because the two primary outcomes are independent, and an improvement in one without the other will be informative.

The subsample of 1500 girls selected to provide daily diary data on school/class attendance and their menstrual cycle over 40 school days at endline provides >98% power to detect a 20% relative reduction on period-days at endline, based on pilot data [6] and ~89% power to detect this difference by district or other equally sized subgroups. From our pilot, we expect >95% of girls to be menstruating at endline, and this is accounted for in the power calculations where relevant.

Revised power calculations were conducted in March 2022 and reported to the IDMEC in April 2022 (report 1), following indication that due to COVID-19 closures and other reasons the harmonic mean school size may be smaller than 60. This showed that a harmonic mean of 40 female students per school at endline provides 80% power to detect a standardised mean difference of 0.2 assuming an ICC of 0.05.

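### Rule 3 of the Benjamini-Hochberg procedure for the two primary outcomes repeats rule 2's condition and contradicts it, so a real effect on one outcome could be declared no evidence

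*SAP*

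**What the plan says.** SAP section 6.2 commits to a multiplicity adjustment for the primary outcomes: "we shall adjust the Type 1 error for multiple testing using the Benjamin-Hochberg (BH) procedure". It applies this "for the two primary outcomes considering a false discovery rate (FDR) of 0.05" and spells the procedure out in three rules.

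- **Rule 1:** if the larger p-value is at most 0.05, both endpoints are supported.
- **Rule 2:** "if the larger p-value >0.05, then the smaller p-value should be" at most 0.025 for the endpoint it belongs to to be supported.
- **Rule 3:** "3) if the larger p-value >0.05, then there is no evidence for both endpoints".

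The section opens by explaining that the two outcomes work through different mechanisms, "so an improvement in one without the other will be informative". Section 2.3 (Sample size) makes the same point: "an improvement in one without the other will be informative". Section 6.2 also says that, despite the procedure, "interpretation of the intervention effect will focus on effect sizes and confidence intervals rather than p-values".

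**The concern.** Rules 2 and 3 are triggered by the same event, a larger p-value above 0.05, and rule 3 says nothing about the smaller p-value. Whenever the smaller p-value is at most 0.025, rule 2 supports one endpoint and rule 3 supports none. Nothing in the section says which rule prevails.

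These three rules are the only multiplicity rule the SAP states for its primary outcomes. The result on which they clash, a clear effect on one outcome and not on the other, is the very case that sections 2.3 and 6.2 say should count. If rule 3 prevailed, both outcomes would have to reach p ≤ 0.05 before either could be claimed. If the choice between the rules were left until the p-values were known, it would be a post hoc decision on a primary endpoint.

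**Working it through.** **1. The thresholds.** The Benjamini-Hochberg step-up critical values are i × q / m. With m = 2 tests and q = 0.05 (section 6.2):

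- i = 1: 1 × 0.05 / 2 = 0.025, for the smaller p-value
- i = 2: 2 × 0.05 / 2 = 0.05, for the larger p-value

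Both agree with the SAP. The procedure supports neither endpoint only when the larger p-value is above 0.05 **and** the smaller is above 0.025. Rule 3 omits the second half.

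**2. Where the rules disagree.** Number of endpoints supported:

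| Smaller p | Larger p | Benjamini-Hochberg (rules 1 and 2) | Rule 3 taken literally |
|---|---|---|---|
| 0.001 | 0.30 | 1 | 0 |
| 0.02 | 0.06 | 1 | 0 |
| 0.03 | 0.06 | 0 | 0 |
| 0.03 | 0.04 | 2 | 2 (rule 1 applies) |

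**3. The plan's power.** Inputs from section 2.3: 60 schools (30 per arm), standardised mean difference 0.2, ICC 0.05, type 1 error 0.05 (taken as two-sided), and a harmonic mean of 60 girls per school, or 40 in the revised calculation. The variance of the difference is (2/30) × (0.05 + 0.95/m), where m is now the number of girls per school.

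- m = 60: variance 0.00439, standard error 0.0662, noncentrality 0.2/0.0662 = 3.02
- m = 40: variance 0.00492, standard error 0.0701, noncentrality 0.2/0.0701 = 2.85

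With a noncentral t on 58 degrees of freedom:

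| | m = 60 | m = 40 |
|---|---|---|
| Power at 0.05 | 0.843 | 0.801 |
| Power at 0.025 | 0.762 | 0.708 |

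The first row reproduces the 84% and 80% in section 2.3.

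**4. One outcome truly improved, the other not, tests independent.** Under the correct procedure the real effect is declared if its p-value is at most 0.025, or if it lies between 0.025 and 0.05 and the null outcome also falls at or below 0.05 (probability 0.05).

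- m = 60: 0.762 + (0.843 − 0.762) × 0.05 = 0.766
- m = 40: 0.708 + (0.801 − 0.708) × 0.05 = 0.713

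Under literal rule 3 both p-values must be at most 0.05.

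- m = 60: 0.843 × 0.05 = 0.042
- m = 40: 0.801 × 0.05 = 0.040

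**5. Both outcomes truly improved, tests independent: chance of at least one claim.** Correct procedure: 1 − (1 − power at 0.025)² + (power at 0.05 − power at 0.025)².

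- m = 60: 1 − 0.238² + 0.081² = 0.950; literal rule 3: 0.843² = 0.711
- m = 40: 1 − 0.292² + 0.093² = 0.923; literal rule 3: 0.801² = 0.642 (0.641 before rounding)

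**6. Neither outcome improved.** The chance of any claim is 1 − 0.975² + 0.025² = 0.05 under the correct procedure and 0.05² = 0.0025 under literal rule 3.

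**7. The corrected rule.** With the condition on the smaller p-value added to rule 3, each of 1,000,000 simulated pairs of p-values fell under exactly one of the three rules, and the decisions are those of Benjamini-Hochberg.

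**The case against.** The strongest reply is that this is a drafting slip with a recoverable meaning. The section names the method, cites its source and gives both correct thresholds, and rules 1 and 2 alone already settle every case. Nothing says that rule 3 overrides rule 2; reading it that way would empty rule 2 and contradict the section's opening sentence. Rule 3 could even be read as saying only that the joint claim for both endpoints fails. Interpretation is to rest on effect sizes and confidence intervals, and no estimate, interval or p-value changes with rule 3. The power figures also assume independent tests, which different causal mechanisms do not establish for outcomes measured in the same girls and schools.

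Much of this stands. The intent is recoverable, the 4% is a worst case rather than a forecast, and the independence assumption is a real limit on the figures. But the joint-claim reading is the less natural one and would leave rule 3 adding nothing to rule 1. The emphasis on confidence intervals does not say which rule prevails, and the plan still commits to the adjustment. The contradiction lies in the wording and does not depend on any power figure.

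**Conclusion.** The concern holds. Rule 3 is wrong as written: it contradicts rule 2 whenever the larger p-value exceeds 0.05 and the smaller is at most 0.025, and it departs from the method the SAP names and from the SAP's stated aim.

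If it were applied literally, the chance of declaring a real effect confined to one outcome would fall from 76.6% to 4.2% (60 girls per school) or from 71.3% to 4.0% (40 per school). With both effects real, the chance of at least one claim would fall from about 95% to 71%, or from about 92% to 64%. These figures rest on the inputs of section 2.3, a two-sided test on 58 degrees of freedom and independent test statistics. Under the Benjamini-Hochberg procedure as correctly stated, none of this power is lost.

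**What to change.** Add the missing condition to rule 3, for example: *where the larger p-value is above 0.05 and the smaller p-value is above 0.025, neither endpoint is supported*. Rules 1 and 2 can stay as they are.

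The cost is one clause of SAP text, with no change to data, design, models or thresholds. It should be made before anyone sees results by arm. SAP version 1.2 (2024-01-16) is later than the endline assessments of June to August 2023, and the document does not show whether unmasking has taken place. If it has, the correction should be dated and reported as a clarification made afterwards.
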